4.5.3.2. Vital Signs

Summaries of grade increase in temperature, systolic blood pressure (SBP) and diastolic blood pressure (DBP) will be provided separately. These summaries will display the number and percentage of participants with any grade increase, increase to Grade 2, increase to Grade 3 and increase to Grade 4 (for temperature only), for worst case post-baseline only. The summaries will be produced for worst case post baseline only. The DAIDS grading system Version 2.1 [National Institute of Allergy and Infectious Diseases. Division of AIDS, 2017], will be used for grading: The grade definition for temperature is: Grade 1 (38.0°C – <38.6°C), Grade 2 (38.6°C – <39.3°C), Grade 3 (39.3°C – <40.0°C), Grade 4 (>=40.0°C). The grade definition for SBP is: Grade 1 (140-159), Grade 2 (160-179), Grade 3 (>=180). The grade definition for DBP is: Grade 1 (90-99), Grade 2 (100-109), Grade 3 (>=110). DAIDs does not include a Grade 0, please refer to the Output and Programming Specification (OPS) for instruction on how to present values that don't meet the criteria for Grade 1+. Subjects with missing baseline values are assumed to have a normal baseline value.

4.6. Other Analyses

4.6.1. Subgroup analyses

Descriptive summary by subgroups as defined in Table 7 will be provided. Summary statistics (n (%)) for the number of SVR responders will be reported by subgroups for each treatment arm. No statistical comparison between subgroups will be performed.

If the number of participants is too small (<5 per subgroup category) within a subgroup, then the subgroup categories may be redefined prior to unblinding the study.

In addition, selected summaries will be presented by baseline analysis stratification factors and/or subgroups, as detailed in the OPS.

Table 7 Subgroups & Subgroup Categories

Subgroup	Categories
HBeAg Status	Positive or Negative
Baseline HBsAg (log10 IU/mL)	Low (≤ 3 log10 IU/mL), High (>3log10 IU/mL)
	<=3, >3-3.5, >3.5-4 and >4
	Low (<=3000 IU/mL), High (3000 IU/mL)
Baseline HBV DNA level (log10	For participants on stable nucleos(t)ide therapy:
IU/mL)	- Not applicable
	For participants not currently on nucleos(t)ide therapy:
	<=6;>6
	<=4, >4 - <=6, >6
Age group	EMA: <18 ; $\ge 18-64$; $\ge 65-84$, ≥ 85
	FDAAA: ≤18; ≥19-64; ≥65
	Clinical and Epi (Group 1): <50, ≥50

Subgroup	Categories
Sex	Male, Female
Race	American Indian or Alaska Native; Asian; Black or African American; Native Hawaiian or Other Pacific Islander; White
	If enough data are available (≥5 patients per group per arm) Asian may be further categorised as Asian – Central/South Asian Heritage; Asian – Japanese Heritage; Asian – East Asian Heritage; Asian – South East Asian Heritage or a combination of these, and White may be further categorises as White – Arabic/North African Heritage; White – White/Caucasian/European Heritage
Baseline viral genotype	For participants with CHB on stable nucleos(t)ide therapy:
	 B; C; Other, Unknown For participants with CHB not currently on nucleos(t)ide therapy: B; C; Other; Unknown. If enough data are available (≥5 patients per group per arm), Other may be further categorised into observed genotypes
Baseline substitution in the binding site	For participants with CHB not currently on nucleos(t)ide therapy only: Present; Absent
Baseline BMI	<30, ≥30
Baseline ALT	<=ULN; >ULN
Baseline METAVIR Fibrosis Score	If enough data are available (≥5 patients per group per arm): F0 – F2 ; F3
For on-NUC population only: Time on current NUC	<3 years; >=3 years
For on-NUC population only: Type of NUC	TAF&TDF vs Entecavir vs Other
For Treatment naïve group only: Immune tolerance	For participants with CHB not currently on nucleos(t)ide therapy: Immune-tolerant; Not immune-tolerant
	Subjects are defined as immune tolerant if they meet all of the following criteria: Treatment naïve (i.e. no prior medications reported on the Prior Medications CRF), HBeAg positive (>=0.09 U/mL), ALT normal (<= 33 IU/mL in females; <=40 IU/mL in males) and HBV DNA >10^6 IU/mL
Duration of Hep B Infection	<5 years, ≥ 5 years - <10 years, ≥ 10 years - <20 years, ≥ 20 years
Phase of HBV Infection (Strict Criteria)	Phase 1; Phase 2; Other HBeAg-positive; Phase 3; Phase 4; Other HBeAg-negative, where phases are defined as below.
	Phase 1 = HBeAg-positive, ALT <= ULN during screening and at baseline, HBV DNA > 106 IU/ml during screening and at baseline Phase 2 = HBeAg-positive, ALT > ULN either during screening or at baseline, HBV DNA > 104 IU/ml during screening and at baseline Other HBeAg-positive = HBeAg-positive, neither Phase 1 nor Phase 2 Phase 3 = HBeAg-negative, ALT <= ULN during screening and at
	baseline, HBV DNA < 20,000 IU/ml during screening and at baseline Phase 4 = HBeAg-negative, ALT > ULN either during screening or at

Subgroup	Categories
	baseline, HBV DNA > 2,000 IU/ml during screening and at baseline
	Other HBeAg-negative = HBeAg-negative, neither Phase 3 nor Phase 4
Phase of HBV Infection (Loose Criteria)	Phase 1 loose; Phase 2 loose; Phase 3 loose; Phase 4 loose, where phases are defined as below.
	Phase 1 loose= HBeAg-positive, ALT <= ULN during screening and at baseline
	Phase 2 loose = HBeAg-positive, ALT > ULN either during screening or at baseline
	Phase 3 loose = HBeAg-negative, ALT <= ULN during screening and at baseline
	Phase 4 loose = HBeAg-negative, ALT > ULN either during screening or at baseline
HBV RNA level	Target not detected; Target detected
HBcrAg	Low (<= 3 log10 U/mL); High (> 3 log10 U/mL)

4.6.2. Subpopulations to Support Regulatory Consultation

To support consultation with regulators, key study population, efficacy, safety and pharmacokinetic analysis will be repeated in the following subpopulations:

Japan subpopulation: All subjects of Japanese heritage enrolled at sites in Japan

China mainland subpopulation: All subjects enrolled at sites in China Mainland

East Asia subpopulation: All subjects of a relevant Asian heritage (Asian – Japanese Heritage, Asian – East Asian Heritage or Asian – South East Asian Heritage) enrolled at sites in Hong Kong, Taiwan, Japan, South Korea, China mainland.

4.6.3. Concordance of virologic response at Week 6, Week 12, Week 18 and Week 24 and achieving SVR

The concordance of early virologic response (HBV DNA < LLOQ and HBsAg < LLOQ) at on-treatment timepoints of interest with achieving SVR will be explored. Number of participants with an early virologic response (Yes or No) will be cross tabulated with SVR (Yes or No) for on-treatment visits Week 6, Week 12, Week 18 and Week 24 separately. Positive Predictive Value and Negative Predictive Value will be presented, calculated as:

Positive Predictive Value = Number of True Positives / (Number of True Positives + Number of False Positives)

A true positive is defined as a participant with an early response who goes on to achieve SVR. A False positive is a participant with an early response who does not achieve SVR.

TMF-13936631 **CONFIDENTIAL** 209668

Negative Predictive Value = Number of True Negatives / (Number of True Negatives + Number of False Negatives)

A true negative is defined as a participant without early response who does not achieve SVR. A false negative is a participant without early response who goes on to achieve SVR.

The table will be presented separately for each arm, and also for Arms 1, 2, and 3 combined.

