4. STUDY DESIGN

4.1. Overall Design

This is a Phase 2b, multi-center, randomized, partial-blind [Sponsor and Participant blinded], study to assess efficacy and safety of treatment with GSK3228836 in two populations of patients with CHB (1) participants on stable nucleos(t)ide treatment and (2) participants not currently on nucleos(t)ide therapy.

Both populations of patients with CHB will be randomized into one of 4 parallel arms:

- 300 mg GSK3228836 once/week for 24 weeks (plus loading dose of 300 mg GSK3228836 on Day 4 and Day 11);
- 300 mg GSK3228836 once/week for 12 weeks (plus loading dose of 300 mg GSK3228836 on Day 4 and Day 11) followed by step-down in dose of 150 mg (plus placebo to match to maintain participant blinding) GSK3228836 once/week for 12 weeks;
- 300 mg GSK3228836 once/week for 12 weeks (plus loading dose of 300 mg GSK3228836 on Day 4 and Day 11) followed by placebo once/week for 12 weeks;
- Placebo once/week for 12 weeks followed by 300 mg GSK3228836 once/week for 12 weeks (plus placebo loading doses to match on Day 4 and Day 11, no loading dose for GSK3228836 treatment)

After the 24 weeks of dosing with GSK3228836 or placebo, there will be a post-treatment follow-up period of 24 weeks.

Populations will be stratified based on HBsAg level (HBsAg \leq 3 log IU/mL and \geq 3 log IU/mL) and whether participants are HBeAg positive or negative.

The study is a partially blinded study where participants will be blinded to the study treatment. The investigators, site staffs and pharmacist will be unblinded. GSK and contract research organization (CRO) team members will be blinded to participants' study treatment and any potentially unblinding information, unless specified otherwise in the study blinding management plan (e.g., unblinded site monitors).

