4.2.2.1. Visit windowing and multiple measurements at one analysis timepoint

Visit windowing for the primary endpoint will be applied as specified in Table 2 and Table 3 and the windowed results will be used to determine the primary endpoint of SVR. Unscheduled assessments will be included in the analysis window. No imputation of missing data will be performed prior to visit windowing.

If there are multiple values within an analysis window the following rules will be applied:

For the End of '836 Treatment Analysis Timepoint:

1. The latest available assessment in the window will be selected.

For Post '836 Treatment Analysis Timepoints:

- 1. Worst non-missing value in the analysis window will be selected, if values are the same then the value closest to target day will be selected. If there are multiple values equidistant from the target day, the earliest will be selected. If all values within an analysis window are missing, then the result is missing for the analysis window.
- 2. Worst value is defined in the order of: highest actual value, then <LLOQ, and then TND.

Table 2 Primary endpoint analysis windows for Arms 1, 2 and 4

Analysis	Parameter	Target	Analysis	Window	Analysis	Protocol
Set / Domain	(if applicable)	Study Day	Beginning Timepoint	Ending Timepoint	Timepoint	Visit
Efficacy	HBsAg and HBV DNA	162	148	182	End of '836 Treatment	Week 24
		218	183	238	Post '836 treatment Week 8	Off treatment Week 8
		274	239	294	Post '836 treatment Week 16	Off treatment Week 16
		330	295	350	Post '836 treatment Week 24	Off treatment Week 24

Table 3 Primary endpoint analysis windows for Arm 3

Analysis	Analysis Parameter		Analysi	s Window	Analysis	Protocol
Set / Domain	(if applicable)	Study Day	Beginning Timepoint	Ending Timepoint	Timepoint	Visit
Efficacy	HBsAg and HBV DNA	78	64	98	End of '836 Treatment	Week 12
		134	99	154	Post '836 treatment Week 8	Week 20
		190	155	210	Post '836 treatment Week 16	Off treatment Week 4
		246	211	266	Post '836 treatment Week 24	Off treatment Week 12

The primary analysis will be based on planned end of treatment regardless of whether a patient discontinued treatment early.

For the second supplementary estimand described in Section 4.2.4.2, SVR will be measured from actual rather than planned end of treatment and the analysis windows should be amended accordingly. For this estimand, the date of last dose should be treated as the reference date and the rules in Table 4 should be used to determine the endpoint of SVR.

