4.6.4. Association between HBV DNA TND and relapse

In participants who achieve a virologic response (HBsAg < LLOQ and HBV DNA < LLOQ) in the absence of rescue medication at the End of GSK3228836 Treatment visit (Week 12 / Week 24), a cross tabulation of achieving HBV DNA TND / not achieving HBV DNA TND vs. no relapse / relapse at 8, 16 and 24 weeks after end of treatment will be produced. The Off-Treatment timepoints will be based on the time since planned end of GSK836 treatment visit rather than visit labels in the schedule of assessments. The table will be repeated for each arm and overall. Data will also be listed.

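### SAP 4.6.3 pools Arm 3 with Arms 1 and 2 at Weeks 18 and 24, although for Arm 3 those visits fall after active drug and inside the SVR assessment period

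*SAP*

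**What the plan says.** SAP 4.6.3 tabulates response (HBsAg and HBV DNA both below LLOQ) against SVR "for on-treatment visits Week 6, Week 12, Week 18 and Week 24 separately" and reports PPV and NPV. On presentation it says: "The table will be presented separately for each arm, and also for Arms 1, 2, and 3 combined". Its definitions take the response to come before the outcome: "A true positive is defined as a participant with an early response who goes on to achieve SVR". Nothing in the section treats Arm 3 differently at any visit.

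Protocol 4.1 gives Arm 3 12 weeks of active drug, with loading doses "on Day 4 and Day 11) followed by placebo once/week for 12 weeks". SAP 4.2.2.1 therefore has a separate Table 3, "Primary endpoint analysis windows for Arm 3", and states that "the windowed results will be used to determine the primary endpoint of SVR". For the post-treatment windows the rule is: "Worst non-missing value in the analysis window will be selected". SAP 4.2.2.2 then counts a participant as a responder only if both markers are below LLOQ in every window.

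The next section, SAP 4.6.4, handles the difference between arms explicitly. Its off-treatment timepoints are "based on the time since planned end of GSK836 treatment visit rather than visit labels in the schedule of assessments". SAP 4.4.1.2 describes a shorter concordance table (Weeks 6, 12 and 24), also without any arm restriction.

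**The concern.** A concordance table of this kind asks whether suppression seen during treatment predicts what happens afterwards. That requires the predictor to be measured before the outcome period. In Arm 3 the Week 18 and Week 24 results are themselves components of the outcome, so agreement with SVR is partly built in.

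Arm 3 makes up a third of the combined table (66 of 198 planned participants in each population). The combined row has the largest sample and is the one most likely to be quoted as the predictive value of an early response. The SAP version history records that the analysis was requested at the third interim analysis, so someone intends to use it. What is at stake is the reading of these predictive values, not the estimate of SVR in any arm.

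**Working it through.** **1. Visit days.** SAP 6.2.2.1 gives day = 1 + 7(x − 1) for on-treatment Week x, and its off-treatment targets follow 169 + 7(x − 1). These reproduce the target days in SAP Tables 2 and 3: Week 12 = 78, Week 20 = 134, Week 24 = 162, off-treatment Week 4 = 190, off-treatment Week 12 = 246. The landmark visits then fall as follows.

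| Visit | Day | Arm 3 SVR window | Weeks from Day 78 | Arms 1 and 2 SVR window |
|---|---|---|---|---|
| Week 6 | 36 | none | −6 | none |
| Week 12 | 78 | end of treatment (64–98) | 0 | none |
| Week 18 | 120 | post-treatment Week 8 (99–154) | +6 | none |
| Week 24 | 162 | post-treatment Week 16 (155–210) | +12 | end of treatment (148–182) |

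The ±3-day visit allowance (Days 117–123 and 159–165) does not move either late visit out of its Arm 3 window.

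**2. Arm 3.** A result at or above LLOQ at Week 18 or 24 becomes the worst value in its window, the window fails, and SVR fails. So false negatives (FN) = 0 and NPV = TN/(TN + FN) = 100%. Every SVR is a true positive, so PPV = N(SVR)/N(landmark responders). As responders relapse, the denominator shrinks while the numerator stays fixed. Anyone first suppressed after the end-of-treatment window partly offsets this.

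**3. Arms 1 and 2.** Week 18 precedes all their windows. Week 24 lies in the end-of-treatment window, but there the latest assessment is used. Scheduled visits in that window are Days 148, 155, 162, 169 and 176, so Day 162 does not decide SVR when a later result exists. A false negative needs a result at or above LLOQ on Day 162 and one below LLOQ at the last assessment in the window. That is possible but should be rare.

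**4. Pooled NPV.** Let e be 1 − NPV in Arms 1 and 2, and q the share of landmark non-responders from Arm 3. The pooled rate is (1 − q)e. With q = 1/3 it is 2e/3, whatever e is. The documents do not give e; by step 3 it should be close to zero at Week 24.

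**5. Pooled PPV, illustration.** Assumptions, none from the documents: 30% respond at end of treatment in each arm, one third of those sustain for 24 weeks, and relapse hazard is constant. The fraction of Arm 3 responders still suppressed t weeks after stopping is (1/3)^(t/24).

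- Arm 3 PPV: 33% at Week 12; 0.333/0.760 = 44% at Week 18; 0.333/0.577 = 58% at Week 24. Drug effect is unchanged.
- Week 24 counts: Arms 1 and 2 have 132 × 0.30 = 39.6 responders and 13.2 SVR. Arm 3 has 19.8 × 0.577 = 11.4 responders and 6.6 SVR.
- Pooled as planned: 19.8/51.0 = 38.8%. With Arm 3 taken at its own end of treatment: 19.8/59.4 = 33.3%.

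With 30% response kept, Arm 3 durability varied from 10% to 50%, and Arms 1 and 2 durability set at 33% or 50%, the gain over the aligned figure is about 4 to 11 points. Pooled PPV need not exceed the Arms 1 and 2 value. With durability of 10% in Arm 3 and 50% in Arms 1 and 2, the pooled figure is (19.8 + 1.98)/(39.6 + 6.26) = 47.5%, below 50%.

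**6. Simulation check.** Assumptions: exponential onset with mean 40 weeks; a quarter never relapse; the rest relapse on average 10 weeks after stopping (or after onset, if later); onset possible up to 0, 4 or 8 weeks after stopping; durability equal across arms.

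| | Week 18 | Week 24 |
|---|---|---|
| Arm 3 false negatives | 0 | 0 |
| Arm 3 PPV (31.7–31.9% at Week 12) | 36.9–47.8% | 46.5–66.7% |
| Pooled PPV as planned | 33.2–35.0% | 34.5–36.0% |
| Pooled PPV, Arm 3 at Week 12 | 31.7–31.9% | 31.7–31.9% |
| Pooled NPV as planned | 96.4–97.3% | 99.1–100% |
| Pooled NPV, Arm 3 at Week 12 | 95.8–97.2% | 98.4–100% |
| NPV, Arms 1 and 2 alone | 94.2–95.6% | 98.4–100% |

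Scenario by scenario, planned pooling raises NPV by at most 0.7 point over the aligned version. Against Arms 1 and 2 alone the rise is 1.7 to 2.2 points at Week 18 and 0 to 0.7 at Week 24.

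**The case against.** The exposure is limited. The table sits under Other Analyses, has no test or decision rule, and feeds neither the primary estimate nor regimen selection. Arms 1 and 2 are also shown separately, so an unaffected version is on the same page. The on-treatment label is formally correct too: SAP 6.2.3 counts from the last study treatment dose, and Arm 3 receives placebo to Week 24. All of this stands and keeps the point minor. It does not change what the combined row measures.

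A reader might go further and infer that pooled PPV and NPV are both inflated by construction. The documents do not support that. Only the near-absence of Arm 3 false negatives follows from the windows. The PPV shift depends on relapse rates and on the comparator. Protocol 4.3 suggests that longer treatment may be needed for sustained seroclearance; if so, Arm 3 durability could be lower and pooling could pull PPV below the Arms 1 and 2 value, as in the 47.5% example.

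A reader might also take Arm 3 false negatives to be strictly impossible. There are exceptions: SAP 4.6.3 does not say how a missing landmark result is classified, and SVR can be imputed after a wide disruptive event (SAP 4.2.2.2). The Arm 3 visit list in SAP 4.2 and Protocol 9.4.2 also names Week 24 but not Week 18. If only listed visits counted, a Week 18 result would not force failure. However, SAP 4.2.2.1 derives SVR from the windowed results, and Table 3's window includes Day 120.

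Finally, a figure such as 95% NPV in Arms 1 and 2 might be assumed in order to claim a sizeable distortion. No such figure is in the documents, and it is implausible at Week 24, where those arms are inside their own end-of-treatment window.

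**Conclusion.** The point holds, with low impact. For Arm 3 the Week 18 and Week 24 results are part of the SVR definition, so the combined rows do not estimate the predictive value of an on-treatment response. This rests on stated study days and rules, with the exceptions noted for missing and imputed values.

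No size can be given from the documents. The illustrations suggest that the PPV distortion, measured against a treatment-aligned landmark, is a few points and could reach about 11. The NPV effect is probably small, most clearly at Week 24. Whether pooled PPV lies above or below that of Arms 1 and 2 alone is open.

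**What to change.** In SAP 4.6.3, choose one of two rules for the combined table:

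- restrict the Week 18 and Week 24 rows to Arms 1 and 2; or
- define landmarks in all arms by time relative to planned end of GSK3228836, the approach SAP 4.6.4 takes for its off-treatment timepoints. Six weeks before planned end is then Week 18 in Arms 1 and 2 and Week 6 in Arm 3; planned end is Week 24 and Week 12 respectively.

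In either case:

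- footnote the Arm 3 table to say that Weeks 18 and 24 are after active drug and inside the SVR period;
- if Week 12 stays pooled by visit label, note that it is end of treatment for Arm 3 (inside its Day 64–98 window) and mid-treatment for Arms 1 and 2;
- apply the same change to Week 24 in SAP 4.4.1.2.

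The cost is a sentence in each of two SAP sections, two footnotes and a small change to the table programming. No new data are needed.

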4.6.4. Association between HBV DNA TND and relapse

In participants who achieve a virologic response (HBsAg < LLOQ and HBV DNA < LLOQ) in the absence of rescue medication at the End of GSK3228836 Treatment visit (Week 12 / Week 24), a cross tabulation of achieving HBV DNA TND / not achieving HBV DNA TND vs. no relapse / relapse at 8, 16 and 24 weeks after end of treatment will be produced. The Off-Treatment timepoints will be based on the time since planned end of GSK836 treatment visit rather than visit labels in the schedule of assessments. The table will be repeated for each arm and overall. Data will also be listed.

4.6.5. Determining the optimal cut point of baseline HBsAg to predict response

ROC analysis will be used to estimate a single cut-point that can best be used to predict SVR. Baseline HBsAg will be plotted against SVR status and a ROC curve will be produced. A table showing the specificity (1-false positive rate), sensitivity (true positive rate) and accuracy for each cut-off will be presented. The optimal cut-off will be determined from the cut-off with the highest accuracy. The outputs will be displayed for each arm separately, and overall.

False Positive Rate, True Positive Rate and Accuracy are calculated as:

False Positive Rate = number of False Positives (FP) / number with Actual Outcome = Negative (Neg)

True Positive Rate = number of True Positives (TP) / number with Actual Outcome = Positive (Pos)

Accuracy = number of True Positives (TP) + Number of True Negatives (TN) / number with Actual Outcome = Positive (Pos) + number with Actual Outcome = Negative (Neg)

Where counts for FP, TP, TN, Neg and Pos are defined as shown in Table 8.

Table 8 Classification of conditions for ROC analysis

		Predicted Outcome	
		Positive (PPos) (Predicted	Negative (PNeg)
		SVR)	(Predicted No SVR)
Actual	Positive (Pos) (SVR)	True Positive (TP)	False Negative (FN)
Outcome	Negative (Neg) (No SVR)	False Positive (FP)	True Negative (TN)

If the original value <= cut-off then the predicted outcome is positive (i.e. predicted SVR=yes). If original value > cut-off then the predicted outcome is negative (i.e. predicted SVR=no)

4.6.6. Predictors of SVR response

If sufficient data are available, an exploratory analysis will be performed to identify predictors of SVR response.

The following continuous baseline variables will be considered for inclusion in the model, additional clinically relevant variables may be considered:

Age (years), BMI, HBsAg (log10 IU/mL), HBV DNA (log10 IU/mL), HBcrAg (log10 U/mL), HBV RNA (copies/mL), ALT (IU/L), Platelet count, APRI Score, eGFR, Urine Albumin (g/dL), Serum Creatinine (umol/L), ACR (g/mol), Length of Diagnosis (Years)

The following categorical baseline variables will be considered for inclusion in the model, additional clinically relevant variables may be considered:

Sex (Male; Female), Race (American Indian or Alaska Native; Asian; Black or African American; Native Hawaiian or Other Pacific Islander; White), HBsAg (<=3 log10 IU/mL; >3 log10 IU/mL), HBeAg Status (Positive; Negative), HBV Genotype (A, B; C; D, E, Other; Unknown), Metavir Score (F0, F0-F1, F1, F1-F2, F2, F2-F3, F3, F3-F4, F4), Prior Interferon Use (Yes, No), Method of Transmission (Vertical, Horizontal, Unknown, Prefer not to Say and Other), Nucleos(t)ide Use (type of Nucleos(t)ide).

If appropriate, continuous variables may be separated into categories, using the subgroup categories from Section 4.6.1 or another appropriate categorisation (e.g. median split). Additional clinically relevant variables may be considered.

The definition of response for the analyses described in this section is SVR as defined for the primary efficacy analysis.

A summary of the number and proportion of SVR successes will be provided for each category of the variables considered as potential predictors of response. For continuous variables a median split will be used to categorise the data in the summary.

Summary statistics (n, Mean (SD) & 95% CI, Median, Min, Max for continuous variables and n (%) for categorical variables) for potential predictors of response in participants with and without SVR will also be presented by arm and overall.

Summaries will be graphically presented using boxplots (for continuous variables) and Forest style plots (for categorical variables). For boxplots, response (responder vs non-responder) will be shown on the x-axis and baseline characteristic value will be shown on the y-axis. The Forest style plot will show the proportion of participants in each category who have a response.

Summary tables and figures will be presented by treatment arm and overall.

A predictive logistic regression model will be built using a forward stepwise selection approach using the Akaike Information Criterion (AIC). The model will use Firth's penalised likelihood approach to avoid the potential issue of separation [Heinze G, 2002]. Analysis stratification values (HBsAg (<=3 log10 IU/mL; >3 log10 IU/mL), HBeAg Status (Positive; Negative)) will be included in the model, regardless of their impact on AIC. The order in which other covariates will be included in the algorithm will be determined prior to fitting the model, and will be based on clinical understanding of the most relevant / readily available predictors of response. Variables with a high proportion of missing data at baseline (e.g. data missing for >10% participants) will not be included in the model selection procedure. The final model will be the model with the minimum AIC. All arms will be included in a single model and arm will be included in the model. If there are enough SVR successes in a single arm (>= 5 SVR success in an arm), the model selection process will be repeated including data from the single arm only.

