4.1.2. Baseline Definition

For all endpoints (except as noted in baseline definitions) the baseline value will be the latest pre-dose (GSK or placebo) assessment with a non-missing value, including those from unscheduled visits. If time is not collected or time of assessment equals that of the first dose, Day 1 assessments are assumed to be taken prior to first dose and used as baseline. If there are multiple assessments collected at the same scheduled time, the average of these assessments will be used as the baseline.

Unless otherwise stated, if baseline data is missing no derivation will be performed and baseline will be set to missing.

Baseline of eGFR and serum creatinine is defined as the mean of all pre-dose values, from screening to Day 1 pre-dose assessment.

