5. SAMPLE SIZE DETERMINATION

Approximately 440 participants are planned to be randomly assigned to study intervention.

For each population, there will be approximately 66 participants assigned in each of the first three arms. There will be approximately 22 participants assigned in the fourth arm.

It is assumed that the number of responders follows a Binomial distribution, with a weakly informative prior (Beta (0.5, 0.5)) for the true response rate. The precision for a range of response rates with 95% credible intervals are shown in Table 10.

Table 10 95% Credible Interval of Response Rate by Sample Size

Sample size per arm	Number of responders	Response rate	95% credible interval*
22	2	9%	1% – 23%
	3	14%	3% - 30%
	4	18%	5% - 36%
	5	23%	8% - 41%
	6	27%	11% - 46%
66	6	9%	3% - 17%
	9	14%	6% - 23%
	12	18%	10% - 28%
	15	23%	13% - 33%
	18	27%	17% - 38%

^{*95%} highest posterior density interval

The lower bounds of 95% credible intervals will exclude the historical placebo response rate of 3% if observed response rate is greater than or equal to 14% in arms 1-3 or 18% in arm 4.

The posterior probabilities that the true sustained virologic response rate is greater than a range of response rates will be calculated from the implied Beta posterior, given the actual number of responders observed.

The operating characteristics based on at least 75% posterior confidence that the true rate exceeds a threshold of interest, are shown in Table 11, for various sample sizes, and true cure rates. The operating characteristics shown are based on a Bayesian model without consideration of baseline analysis stratification factors and expected to be similar to operating characteristics from the hierarchical model defined in Section 4.2.2.

Table 11 End of Study Operating Characteristics by Sample Size

Criterion	Sample Minimum size per number (%) arm of		Probabili	ty of Meeting Assun	Criterion Und	er Various
		responders required to meet Criterion	True Resp Rate=5%	True Resp Rate=20%	True Resp Rate=25%	True Resp Rate=30%
Probability (true	22	5 (23%)	0%	46%	68%	84%
response	44	9 (20%)	0%	53%	81%	91%
rate>15%)>75%	66	12 (18%)	0%	69%	93%	99%
	88	16 (18%)	0%	71%	95%	100%
Probability (true	22	6 (27%)	0%	27%	48%	69%
response	44	11 (25%)	0%	25%	56%	81%
rate>20%)>75%	66	16 (24%)	0%	23%	60%	88%
	88	21 (24%)	0%	22%	64%	92%
Probability (true response rate>25%)>75%	22	7 (32%)	0%	13%	30%	51%
	44	13 (30%)	0%	9%	29%	58%
	66	19 (29%)	0%	6%	28%	63%
	88	25 (28%)	0%	4%	27%	67%

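### SAP 4.6.6 picks SVR predictors by minimum AIC without requiring compared models to use the same participants, and repeats the search in single arms with as few as 5 responders

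*SAP*

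**What the plan says.** SAP 4.6.6 plans an exploratory logistic model for SVR, with Firth penalisation against separation, built by forward selection on AIC. The HBsAg and HBeAg strata "will be included in the model, regardless of their impact on AIC". The order in which the other covariates are tried is fixed before fitting, on clinical grounds. "The final model will be the model with the minimum AIC".

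For missing covariates the only rule is that "Variables with a high proportion of missing data at baseline (e.g. data missing for >10% participants) will not be included in the model selection procedure". That 10% limit is an example, so covariates with some missing values stay in the search. The section gives no imputation, no complete-case set and no rule on which participants enter each comparison. SAP 4.1.2 adds: "Unless otherwise stated, if baseline data is missing no derivation will be performed and baseline will be set to missing".

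The main fit is pooled: "All arms will be included in a single model and arm will be included in the model". Then: "If there are enough SVR successes in a single arm (>= 5 SVR success in an arm), the model selection process will be repeated", using that arm alone. No validation or optimism correction is planned.

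**The concern.** AIC values can be compared only between models fitted to the same observations. Each participant contributes to minus twice the log-likelihood, so dropping participants lowers AIC whether or not the added covariate predicts anything. A minimum-AIC rule applied across different subsets therefore leans towards incompletely recorded covariates.

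The single-arm repeat is a separate problem. A search over a long list of candidates, on as few as five events and on top of two forced terms, will find predictors in noise and fit them almost perfectly in-sample. Firth penalisation deals with separation, not with optimism from selection.

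What is at stake is which baseline characteristics the report names as predictors of SVR.

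**Working it through.** **Inputs from the documents.** SAP 5 states that "there will be approximately 66 participants assigned in each of the first three arms", with about 22 in arm 4. Populations are analysed separately (SAP 4.1), so the pooled model has 3 × 66 + 22 = 220 participants. SAP 4.6.6 lists 14 continuous and 9 categorical candidates. Two of the categorical ones are forced, which leaves 14 + 7 = 21.

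**Assumptions not in the documents.** SVR rates of 5–20%; 60% with HBsAg above 3 log and 30% HBeAg positive; independent noise covariates missing completely at random at 0–10%; AIC computed from the ordinary log-likelihood at the Firth estimates.

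**The plan's own figure.** SAP 4.6.6 gives no numerical result to reproduce. As a check on the arm size, the SAP Table 11 row for n = 66 and at least 12 responders recomputes to 69.1%, 92.7% and 99.0% at true rates of 20%, 25% and 30%, against the stated 69%, 93% and 99%.

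**Step 1: deviance lost per dropped participant.** This is about −2[p ln p + (1 − p) ln(1 − p)]. At p = 0.10 it is −2[−0.230 − 0.095] = 0.65; at p = 0.05 it is 0.40. AIC charges 2 for one extra coefficient. With N = 220:

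| Missing | Participants lost | AIC fall, SVR 10% | AIC fall, SVR 5% |
|---|---|---|---|
| 1% | 2.2 | 1.4 | 0.9 |
| 2% | 4.4 | 2.9 | 1.7 |
| 5% | 11 | 7.2 | 4.4 |
| 10% | 22 | 14.3 | 8.7 |

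At 10% SVR the artefact alone outweighs the penalty from 2% missing upward.

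**Step 2: one noise covariate, pooled model, each model on its own rows.** By simulation with both strata and arm in the model, at 10% SVR the noise covariate lowers AIC in about 52%, 89% and 100% of runs at 2%, 5% and 10% missing. A second set of runs gave 55%, 92% and 100%, and 39% at 1% missing. At 5% SVR the figures for 1%, 2%, 5% and 10% missing are 28%, 32%, 64% and 93%. On common rows the rate is about 12–19% whatever the missingness, in line with P(χ² on 1 df > 2) = 15.7%.

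**Step 3: a whole search.** Ten noise covariates tried in a fixed order, pooled, 10% SVR:

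| Missing in each | Selected, own rows | Participants left in final model | Selected, common complete cases | Participants in that set |
|---|---|---|---|---|
| 0% | 1.65 | 220 | 1.65 | 220 |
| 2% | 5.2 | 195 | 1.5 | 179 |
| 5% | 7.9 | 144 | 1.6 | 132 |
| 10% | 9.1 | 83 | 1.4 | 76 |

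**Step 4: single arm, 5 responders of 66, nothing missing.** Two forced terms already mean 5/2 = 2.5 events per coefficient. With 10 noise candidates, 10 × 0.157 = 1.6 selections are expected, with probability 1 − 0.843^10 = 82% of at least one; simulation gave 1.55 and 77%. With 18 candidates the expectation is 18 × 0.157 = 2.8, with 1 − 0.843^18 = 95%; simulation gave 3.5 spurious predictors, at least one in 95% of runs, and an apparent AUC of 0.99. With 20 responders, 3.8 noise covariates were still selected. An arm of 66 reaches five responders with probability 23% at 5% SVR, 80% at 10% and 99.9% at 20%.

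**Step 5: cost of complete cases over all 21 candidates.** With independent missingness the complete share is 0.98^21 = 65%, 0.95^21 = 34% or 0.90^21 = 11%, which is about 144, 75 or 24 of 220.

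**The case against.** The strongest reply is that the SAP does not say candidates are fitted on their own rows. It is silent, and a careful programmer might fix one set. That stands: the missing-data bias is conditional, and the firm statement is that the plan leaves it open.

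Missingness may also be low. HBsAg, HBV DNA, ALT, platelets, renal function and urine ACR are eligibility tests (Protocol 5.1 and 5.2), APRI is done at screening (Protocol Table 1), and SAP 4.1.2 takes the latest non-missing pre-dose value. Genotype and transmission route have an unknown category. This largely stands. Material gaps are plausible mainly for HBV RNA and HBcrAg, which have no screening sample, and for time since diagnosis.

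The pre-set order of entry is a real safeguard against a data-driven order, but it does not fix the rows; the search in step 3 also used a fixed order.

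The candidates are neither independent nor all relevant in both populations (nucleos(t)ide type does not apply off therapy), so the counts of spurious predictors are indicative. No AUC is planned for this model; it serves here only to measure apparent fit.

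A reader might infer that the reported predictors will reflect data completeness rather than biology, or that this model will choose the next study's population. The documents support neither. They give no missingness rates and no rule on rows, and assign the model no such role. Protocol 2.1 says only in general terms that the study supports later ones.

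**Conclusion.** The concern holds in two parts. First, SAP 4.6.6 permits AIC to be compared across different participants. If that happens, then at N = 220 and 10% SVR a noise covariate is favoured about 52% of the time at 2% missing and 89% at 5%, instead of about 16%. The effect is smaller at 1% missing or 5% SVR. Second, whatever the missingness, the 5-responder trigger allows a search that will usually report noise with a near-perfect apparent fit. AIC admits about 16% of noise covariates in the pooled model too; the single arm is worse because those coefficients rest on so few events.

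The sizes depend on the assumed SVR rates, strata mix, random missingness and independent noise. They also assume the ordinary log-likelihood, which the SAP does not specify. With the Firth-penalised likelihood, noise lowered AIC in 61–100% of runs even on common rows.

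The analysis is exploratory, runs only if data suffice, and leaves the primary SVR estimates untouched. The impact is limited to which predictors are reported.

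**What to change.** 1. State in SAP 4.6.6 that every AIC comparison uses identical participants, through either one baseline-imputed dataset used at every step or a short, pre-fixed candidate list with its complete-case set. Complete cases across all listed candidates could lose far more than a few percent (step 5).
2. Delete the single-arm model-selection repeats and keep the descriptive summaries by arm that the section already plans. Raising the threshold to 20 responders would not cure the problem (step 4).
3. Report bootstrap optimism-corrected performance, repeating the whole selection in each resample.

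The cost is a few sentences of SAP text and modest programming. No new data and no design change are needed.
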